- Comparison of adverse events and Emergency Department (ED) visits between the two groups. Will be determined by reviewing the patient's record to identify adverse events as defined below. Informed consent will include consent to obtain outside ED records; as this is standard practice for patients seen in ED during perioperative/postoperative period.
- Actual time spent on phone call during postoperative telephone follow up compared to time spent in clinic follow up measured in minutes.
- Correlation, between groups, of overall patient's satisfaction with subjective measures, complications, demographics, and travel distance.

VIII. Data Collection:

At the initial visit, once eligibility status is determined and consent is obtained, data collection form will include demographics, distance traveled, complications, and number of ED visits, type of surgery performed etc. Also patients will complete three postoperative patient satisfaction questionnaires at the six-week postoperative clinic visit. This will include the Patient Satisfaction Questionnaire (PSQ) 18 Short Form, a validated questionnaire. Also will include the Patient Global Impression of Improvement (PGII), a validated questionnaire. And a three-question survey about patient satisfaction with the postoperative experience, not validated. All six -week visits will be in person. The questionnaires will be completed before the physician interviews the patient. These questionnaires will be stored in a locked filing cabinet and later transferred by the PI to an excel spreadsheet stored on a password-protected computer. Additionally, pertinent medical information will be extracted from the patient's medical chart, de-identified, and transferred to the an excel spreadsheet after surgery by a member of the study team, including socio-demographic data, perioperative and postoperative details, adverse events, and ED visits.

Adverse events are defined based on previous studies [4, 5,]

- bladder injury
- ureteral injury
- bowel injury

- operative estimated blood loss >500mL
- reoperation < 30 days
- hematoma
- pelvic abscess
- vaginal cuff cellulitis
- ileus
- small bowel injury
- transfusion
- pulmonary
- cardiac
- neurological injury
- urinary tract infection (culture proven, urinalysis with presence of leukocyte esterase, nitrites, or blood, symptoms of infection)
- pyelonephritis
- urinary retention (more than 6 week postoperative)
- mesh erosion
- incisional hernia
- wound complication

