- reoperation for complication of surgery
-

IX. Sample Size:

Sample sizes of 71 in Group 1 and 71 in Group 2 achieve 80% power to detect a non-inferiority margin difference between the group proportions of -0.12. The traditional office visit group proportion is 0.87. The Telehealth group proportion is assumed to be 0.75 under the null hypothesis of inferiority. The power was computed for the case when the actual Telehealth group proportion is 0.90. The test statistic used is the one-sided Z test (unpooled). The significance level of the test is 0.025.

X: Proposed Analyses:

Data analyses will be performed at the University of South Florida in Tampa, Fl. Data management and analyses will be conducted using SAS version 9.4 (SAS Institute, Inc, Cary, North Carolina). Subject demographic characteristics such as age, distance traveled, surgical procedures, ED visits will be summarized by standard descriptive statistics (e.g. means and standard deviations or median (range) for continuous variables and percentages for categorical variables. The difference between groups will be compared using the chi-square test or t-test, as appropriate. Logistic linear regression will be used to evaluate independent predictors for patient satisfaction. A p-value <0.05 will be considered statistically significant.

VIII. Confidentiality

At all times, appropriate measures will be taken to protect the confidentiality of all study participants in accordance with HIPAA guidelines. Patients will be approached for recruitment in private patient exam rooms. Once enrolled, all patients will be administered a study ID number starting with 1 and proceeding numerically. A master link between the individual subjects and their study ID number will be stored in a secure location (on a password-protected computer in the Urogynecology Fellows' office). All data collection forms (DCF) and stored patient information will only contain the study ID number. Charts will be reviewed in a secure location at all times. Upon completion of the data collection period, all information will be entered into an excel spreadsheet on a password-protected computer for data analysis.

IX Safety

This a voluntary study. Patients have the right to refuse to participate.

Data and Safety Monitoring

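### The adverse-event list behind the safety comparison has no entry for unplanned readmission, death or other events, so some serious outcomes would go uncounted

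*Combined protocol and SAP*

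**What the plan says.** Section II.B makes the safety of telephone follow-up a secondary aim, and section V names patient safety among the things on which the arms are compared. Section VII.B gives the outcome: "Comparison of adverse events and Emergency Department (ED) visits between the two groups". Adverse events are found by chart review "to identify adverse events as defined below". For emergency visits the same section adds that "Informed consent will include consent to obtain outside ED records".

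The definition is the bulleted list in section VIII (Data Collection), said to rest on two earlier studies. It includes both a general bowel-injury entry and "small bowel injury", and both "reoperation < 30 days" and "reoperation for complication of surgery".

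Three other places bear on the point:

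- Section VI.B lists a Grade 3 complication, and attending no postoperative visit, as exclusion criteria.
- The Data and Safety Monitoring text allows exclusion criteria to be met after surgery. Those women then appear among the excluded in the CONSORT diagram.
- Section X (Proposed Analyses) names a chi-square or t-test as appropriate. It does not say whether women or events are the unit for adverse events.

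**The concern.** The telephone arm omits vital signs and physical examination at two weeks (section VI.C). The plausible harm is a complication recognised late, and such a complication may end in a hospital admission. A safety outcome for this trial should be able to record an admission or a death whatever its cause. As the outcome is tied to a fixed list, an event without an entry is not counted, however serious it is. A statement that the telephone visit is a safe alternative would then rest on a measure that need not register an admission or a death.

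**Working it through.** No planned figure depends on this list. The only design calculation is for satisfaction, and it reproduces: n = (1.960 + 0.842)² × (0.87×0.13 + 0.90×0.10) / (0.03 + 0.12)² = 70.8, so 71 per arm. The rest of the check is a comparison of passages.

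**1. Is the list closed?** Section VII.B limits adverse events to those defined in the list. The list has 21 entries and none is a catch-all. Other parts of the protocol mention complications and safety issues in general terms, but none adds an entry to the compared outcome. In the text available to me the list ends in an empty bullet. I do not treat that as an omission, but the sponsor should confirm that nothing was meant to stand there.

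**2. Which serious events have a route in?**

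| Event | Counted as the plan is written? |
|---|---|
| Admission that begins in an ED | Yes, as an ED visit |
| Direct admission for a listed diagnosis (e.g. abscess, ileus, pyelonephritis) | Yes, under the diagnosis; the admission itself is not recorded |
| Direct admission for an unlisted reason | No |
| Death from a cardiac or pulmonary cause | Possibly, under those broad entries; the death itself is not recorded |
| Death from an unlisted cause, with no ED visit | No |

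**3. Would repairing the list be enough?** No. A Grade 3 complication is defined in section VI.B as one needing surgical, endoscopic or radiological intervention. If that criterion is applied after surgery, a woman reoperated for a complication leaves the comparison, yet reoperation for a complication is itself a listed adverse event. The two passages must be reconciled. Likewise, a woman who dies before any postoperative visit meets the criterion for attending none. Section VI.C also excludes women in the telephone arm who are not reached after two calls, which could include a woman who is in hospital at the time.

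**4. Size.** With 71 women per arm, one uncounted woman changes that arm's event proportion by 1/71 = 1.4 percentage points. The documents give no rate of direct admission or death from unlisted causes, so the expected number cannot be derived from them.

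**5. Overlapping entries.** No two of the 21 entries are worded alike. Small bowel injury is nested within bowel injury. The two reoperation entries overlap in part: one is limited to 30 days with any cause, the other is limited to complications with no time limit. A small bowel injury, or a reoperation before 30 days for a complication, meets two entries. It counts as 2 if entries are summed and as 1 if women with at least one event are compared. The plan does not say which applies.

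**The case against.** The strongest reply is that little is lost. ED visits are a separate outcome, and outside ED records can be obtained. The cardiac, pulmonary, abscess, ileus, transfusion and wound entries cover many reasons for readmission. The investigator reviews safety throughout, and an independent urologist does so three times, neither expressly limited to the list. This is also a secondary outcome. All of that stands, and it makes the gap narrow. It does not close the gap, because monitoring reviews do not add events to the comparison between arms.

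A reader might go further and infer that the list names the same event twice and that the planned chi-square test is therefore invalid. The documents do not support this. One pair is nested and the other overlaps only in part. The ordinary reading of section X is a two-by-two table of women, which double entries cannot affect.

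I checked this by simulation with 400,000 replicates, 71 women per arm, no true difference, and assumed event risks of 0.10, 0.15 and 0.20. The per-woman chi-square at nominal 5% rejected in 4.9% to 5.2% of replicates.

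To see material inflation, one must compare summed records with a count test that the plan does not name, z = (A − B)/√(A + B), where A and B are the records in each arm. Even then the result depends on how many affected women have a doubled record:

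| Affected women with two records (assumed) | Rejection at risk 0.10 / 0.15 / 0.20 |
|---|---|
| 5% | 4.6 / 4.6 / 4.0% |
| 10% | 5.6 / 5.5 / 4.7% |
| 20% | 7.5 / 7.2 / 6.2% |
| 100% | 16.0 / 13.9 / 12.4% |

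Only two kinds of event can be doubled by the overlaps, so the last row does not describe this list. What remains is that the unit of analysis is unstated.

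**Conclusion.** The point holds in a limited form. Followed as written, the safety comparison treats as event-free a woman admitted directly, or who dies, from an unlisted cause. Exclusions after randomization can remove further serious events. This rests on reading the list as closed, which is what section VII.B says, and on the exclusions being applied after surgery, which the monitoring text allows.

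A reader might infer that the trial misses the most serious events in general. That is too strong, because many of them have a partial route in through ED visits or listed diagnoses. The overlapping entries and the unstated unit are missing detail and do not show an error in the test. Severity is minor: neither the primary outcome nor the sample size is touched.

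**What to change.** - **Add two entries to the list in section VIII (Data Collection):** unplanned hospital readmission and death from any cause, each from surgery through the six-week visit.
- **State the safety population:** all randomized women who had surgery, in the arm to which they were assigned, including those excluded from the satisfaction analysis. Reconcile the Grade 3 exclusion with the reoperation entries.
- **Clarify the count:** define or merge the bowel pair and the reoperation pair, keeping the 30-day distinction if it is wanted. State that the comparison is of women with at least one listed event.

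The cost is a few lines in the protocol and the data form. The planned chart review should supply most of the data. The protocol describes consent for outside ED records, so the sponsor should check whether it also reaches admissions to other hospitals. Women excluded after randomization need their charts reviewed over the same period. The downside is that event rates may look slightly less favourable.

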In the setting of urogynecological procedures, the use of telephone follow up is an area that needs to be studied. There is no known standardization about how postoperative follow up visits are conducted after pelvic reconstructive surgery. There is much variation amongst providers concerning when and how postoperative follow up visits are completed. With the advances in robotic and laparoscopic procedures, hospital length of stay has decreased significantly. We now must examine the benefits of minimally invasive surgery as it relates to postoperative follow up. If in person postoperative visits can be replaced with telephone visits, we can possibly increase patient satisfaction. By allowing the patient to have a postoperative visit in the comfort of her own home, we can save her travel costs and travel time. Additionally, in our practice, the in person postoperative visits can ultimately be replaced with procedures and established patient visits, ultimately allowing for more availability for new patient consultations. By evaluating the use of telephone follow up, versus clinic follow up we will show that patient satisfaction with telephone follow up will be unchanged or improved compared to our standard practices.

II. Objective:

A. Primary Aim(s):

- To determine if patient satisfaction with postoperative care with telephone follow up is non-inferior to clinic follow up.

B. Secondary Aim(s):

- To determine if telephone postoperative follow up is a safe alternative to clinic postoperative follow up visits
- To determine if telephone or clinic follow up visits are preferred based on differing demographics (i.e. age, race, distance traveled, outpatient versus inpatient surgery).
- To determine length of visit differences between telephone and clinic follow up.

III. Hypothesis:

For the standard two-week postoperative visit, follow up telephone calls will be non-inferior to traditional office visits. The telephone visit is a safe and efficient alternative to the in person visit following urogynecological procedures.

a. H_0 Traditional office visits are superior to follow up via telephone calls for two-week postoperative visits.

IV. Interventions:

Scheduled telephone call at the two-week postoperative visit completed by the urogynecology clinic nurse.

V. Study Design:

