- Patient who did not attend any postoperative follow up visit

C. Interventions and Recruitment:

The recruitment and consenting process will be performed by an FPMRS fellow or an attending physician and will occur in a private patient exam room at the time of the surgical consultation follow up visit. After obtaining informed consent, the women will be randomized to either a two-week postoperative telephone visit or two-week postoperative clinic visit. The preferred contact phone number and mailing address will be confirmed. The patient will also receive a brief outline summarizing the study and what to expect in laymen terms. These visits typically occur during each of the three attending physicians' clinics. The provider will include that the patient is a study patient in the surgery letter. Once the surgical scheduler confirms that the patient has been enrolled and consented, she will open the next sealed randomization envelope revealing the patient's allocated intervention and schedule the patient's two-week postoperative visit accordingly (telephone follow up or clinic follow up). If the patient is randomized to telephone follow up, the surgical scheduler will again confirm the preferred contact number and mailing address.

Concerning the two-week postoperative follow up visit, if the patient is randomized into the telephone follow up group, she will be contacted, at the pre-scheduled date and time, by the urogynecology clinic nurse. The nurse will utilize a scripted series of postoperative questions, which are consistent with questions asked during our standard postoperative clinic visits. The same nurse will conduct the telephone follow up visits in an effort to maintain consistency. An example of the script is attached.

Any patient responses that are not consistent with a usual postoperative course will be escalated to an in person visit. However, these patients will remain in the group, to which they were originally randomized, for research analysis purposes. If a patient cannot be reached at the time of her scheduled telephone visit, a second

telephone call will be attempted during the same week. If there is still no answer, the patient will be scheduled for an in person visit, the time and date of this visit will be left on the patients voicemail. Patient will be excluded from study. Patients who were found to have recovered satisfactorily based on telephone follow up, will have six -week clinic visit.

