Vital signs and physical examination will be deferred for the patients in the telephone follow up group. The clinic visit will entail questions about common postoperative complications (including fever, nausea/vomiting, pain, urinary symptoms, constipation, etc.). As per usual, vital signs and a focused physical examination will be completed at the clinic visit. All clinic visits will be performed by an FPRMS fellow and/or attending physician. At the end of each visit (telephone and clinic) patient will be reminded about postoperative restrictions as outlined in discharge instructions. The length of duration of both the telephone and clinic visits will be recorded by documenting the start and end time. For the clinic visit the start time will be the time patient is documented as “arrived” status in waiting area and finish time when the physician leaves the room. For the telephone visit, the start time will be at the time the patient answers the phone and finish time when phone call ends. Both clinic and telehealth visits will be documented with progress notes in EMR.

D. Randomization

Eligible patients will be randomized to Arm1 or Arm2 (Telephone follow up or clinic follow up). Permuted block randomization with randomly varying block sizes will be used. Generation of allocation sequences will be performed using a random-number table.

E. Concealment of Treatment Allocation:

The allocation sequence will be generated by our statistician who is neither responsible for patient recruitment or outcome assessment. Sequentially numbered opaque sealed envelopes will be used for concealment of treatment allocation.

F. Blinding:

It is not possible to mask clinical staff or participants, as they will be aware of the follow-up care that is being delivered over the telephone or in clinic. As such this is not a blinded study. The surgical scheduler will open the sealed randomization envelope revealing the patient’s allocated intervention and document this in the patients’ chart. The PI will keep the master link matching the patient to the allocated intervention. The PI is also responsible for entering all collected data into a de-identified excel spreadsheet.

VII. Outcomes

A. Primary:

- Comparison of patient satisfaction as determined by completion of a non-validated, treatment non-specific satisfaction questionnaire between the two groups. Survey will be provided at the six-week follow up visit.

B. Secondary:

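### The time outcome counts only call minutes for women escalated to clinic, so it overstates the time saved by telephone follow-up as randomised

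*Combined protocol and SAP*

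**What the plan says.** All references are to the combined protocol and SAP.

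- **Efficiency claim.** Section III states: "The telephone visit is a safe and efficient alternative to the in person visit following urogynecological procedures". The Introduction gives the practical motive, that "the in person postoperative visits can ultimately be replaced with procedures and established patient visits".
- **Time aim.** Section II.B is narrower: "To determine length of visit differences between telephone and clinic follow up".
- **Escalation.** Section VI.C: "Any patient responses that are not consistent with a usual postoperative course will be escalated to an in person visit". It adds that "these patients will remain in the group, to which they were originally randomized, for research analysis purposes".
- **Unreached women.** After a second failed call in the same week, section VI.C says: "If there is still no answer, the patient will be scheduled for an in person visit". These women then leave the study.
- **Clocks.** Section VI.C times both kinds of visit. For the call, "the start time will be at the time the patient answers the phone and finish time when phone call ends". The clinic clock runs from documented arrival until the physician leaves the room. There is no rule for a woman who has both a call and a clinic visit.
- **Outcomes.** Section VII.B lists adverse events with ED visits, the time comparison ("Actual time spent on phone call during postoperative telephone follow up compared to time spent in clinic follow up measured in minutes"), and correlates of satisfaction. Neither the outcomes nor the Proposed Analyses section mentions escalated visits or other clinic visits between two and six weeks.

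**The concern.** The strategy to which a woman is randomised in the telephone arm is a call plus, for some women, a clinic visit. The time outcome measures the call and leaves out the visit, and the women affected are those for whom the call was not enough. The omission has a known direction: each escalated visit consumes clinic time that the comparison does not charge to the telephone arm.

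What is at stake is the efficiency half of the section III hypothesis. Call minutes against clinic minutes is the only listed outcome that bears on it, and nothing listed measures how many in-person visits the calls replaced. A practice deciding whether to adopt telephone follow-up would need the proportion escalated, and the plan does not commit to reporting it.

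This is separate from the fact that the clinic clock includes waiting time. It would remain if both clocks recorded contact time only.

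**Working it through.** **The plan's own figure.** The only design calculation in the documents is the sample size for satisfaction. The inputs from the Sample Size section are proportions of 0.87 (clinic) and 0.90 (telephone), a margin of 0.12, one-sided alpha of 0.025, 80% power and an unpooled Z test.

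n per group = (1.960 + 0.842)² × (0.87×0.13 + 0.90×0.10) / (0.12 + 0.03)² = 7.849 × 0.2031 / 0.0225 = 70.9, rounded up to 71. Power at 71 is 80.1%.

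The stated 71 per group is reproduced. It does not involve the time outcome, for which the plan gives no calculation.

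**Time outcome: notation.** The documents give none of these values.

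- C = mean call minutes
- V = mean minutes of a clinic visit, taken as the same for an escalated visit
- e = share of the telephone arm escalated

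**Formulas**, counting escalated visits and assuming no further visits in the clinic arm:

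- Saving as the plan would report it: V − C
- Saving per woman as randomised: V − (C + eV)
- Overstatement: eV
- Share of the reported saving lost: eV / (V − C)
- Escalation at which the arms take equal time: e = 1 − C/V

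**Illustration, assuming C = 8 and V = 45.** The reported saving is 45 − 8 = 37 minutes.

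| e | Telephone mean, 8 + 45e | Overstatement, 45e | Saving as randomised | Share lost |
|---|---|---|---|---|
| 10% | 12.5 | 4.5 | 32.5 | about 12% |
| 20% | 17.0 | 9.0 | 28.0 | about 24% |
| 30% | 21.5 | 13.5 | 23.5 | about 36% |

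The arms take equal time at e = 1 − 8/45, about 82%.

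**Range over other assumed durations**, C from 5 to 15 and V from 30 to 90 minutes:

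| e | Smallest share lost (C = 5, V = 90) | Largest share lost (C = 15, V = 30) |
|---|---|---|
| 5% | 4.5/85 = 5% | 1.5/15 = 10% |
| 10% | 9/85 = 11% | 3/15 = 20% |
| 20% | 18/85 = 21% | 6/15 = 40% |
| 30% | 27/85 = 32% | 9/15 = 60% |

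Equal time is reached between e = 1 − 15/30 = 50% and e = 1 − 5/90 = 94%.

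**Further visits in the clinic arm.** If clinic-arm women have f additional visits each, of the same length, the overstatement becomes (e − f)V. The plan builds extra visits into the telephone arm through escalation and is silent on rechecks in the clinic arm, so f is unknown. The same counting rule is therefore needed in both arms.

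**The case against.** The strongest reply is that the outcome matches its aim. Section II.B asks about length of visit, section VI.C defines a clock for each kind of visit, and section VII.B compares them. That stands: per-visit length is a legitimate description and need not be removed. It answers a different question from section III, which concerns the telephone strategy as an alternative to the clinic visit.

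A second reply is that the data will exist. Section VI.C times both kinds of visit and documents both in the EMR, and the Data Collection section extracts postoperative details from the chart. A reader might infer that the trial could not reveal a high escalation rate; the documents do not support that. The gap is that no outcome or rule is pre-specified. Available data make the repair cheap but do not make it part of the plan.

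Third, the efficiency wording is one sentence of the hypothesis, and freed appointments are background motive. The primary question is satisfaction. This also stands, and it limits the weight of the point.

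Fourth, clinic-arm women may need rechecks too. A reader might infer that appointments saved fall one-for-one with escalation. That would require no further visits in the clinic arm, which the documents do not say. Charging extra visits to the telephone arm alone would bias the comparison the other way.

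**Conclusion.** The point holds as a limited one. Escalated women are analysed in the telephone arm, only their call minutes are counted, and the added visit is not an outcome. Followed as written, the plan overstates the time saved per randomised woman by the escalated share times the length of the escalated visit, less any additional visits in the clinic arm. With the assumed 8 and 45 minutes, that is 4.5, 9 or 13.5 minutes of a reported 37 at 10%, 20% or 30% escalation. These are illustrations only; the documents supply neither durations nor an escalation rate.

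Two stronger readings should be resisted. A reader might infer that the result is wrong by a factor of 1.6 to 2.7, by dividing telephone means of 12.5 to 21.5 by the 8-minute call. That compares the telephone arm with itself, whereas the outcome is a contrast between arms. A reader might also infer that telephone saves no time. On the same assumptions it stays shorter until about 82% are escalated.

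The unreached women, who are booked for a clinic visit and excluded, are a related omission in the same direction, but a separate matter. The satisfaction comparison, its margin and the 71 per group are unaffected.

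**What to change.** In section VII.B:

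1. Keep minutes per call and per clinic visit as a description, serving the section II.B aim.
2. Add a comparison by randomised arm of total follow-up minutes per woman: the two-week contact plus any additional in-person visit before the six-week visit, counted the same way in both arms.
3. Report the proportion of the telephone arm escalated to an in-person visit.
4. Report the number of unscheduled clinic visits before six weeks in each arm.

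Confirm in section VI.C that escalated and unscheduled visits are timed by the same rule as scheduled clinic visits, and add these visits to the items listed under Data Collection. The escalation rule itself does not change.

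The cost is a few sentences and a little more chart extraction, with no extra patients. The downside for the investigators is a less favourable time difference for telephone.
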